1.2. Study Design

Study KDAF is a Phase 2b, randomized, double-blind, placebo-controlled study to determine the appropriate dose and dosing frequency of peresolimab in adult participants with moderately-to-severely active RA.

[figure not shown]
This study includes a

- Period 1: screening period occurring approximately 1 to 42 days prior to Period 2
- Period 2: 12-week double-blind, placebo-controlled treatment period
- Period 3: 48-week double-blind treatment period, and
- Period 4: posttreatment follow-up period occurring 4 and 12 weeks from last treatment period visit (Week 60) or Early Discontinuation Visit.

See the Schedule of Activities (SoA) in the protocol for visit schedule, procedural and assessment details.

In the remainder of this statistical analysis plan (SAP), the first 12 weeks in Period 3 (that is, Weeks 12 to 24) will be referred as Period 3A and the last 36 weeks in Period 3 (that is, Weeks 24 to 60) as Period 3B for an analysis purpose. Combined Periods 2 and 3 will be referred as the Treatment Period (Weeks 0 to 60).

Figure KDAF.1.1 describes the study design for the treatment periods (Periods 2 and 3).

[figure not shown]

Abbreviations: CDAI = Clinical Disease Activity Index; SC = subcutaneous injection; Q4W = every 4 weeks; Q12W = every 12 weeks.

Note: At Week 12, participants receiving placebo Q4W will begin receiving either 400 mg or 1000 mg peresolimab Q4W. At Week 24, participants receiving 400 mg or 1000 mg peresolimab Q4W may be switched to Q12W dosing following assessment of CDAI scores.

Figure KDAF.1.1 Study design.

Participant population

Treatment period design

- 100 mg of peresolimab every 4 weeks (Q4W)
- 400 mg of peresolimab Q4W
- 1000 mg of peresolimab Q4W
- placebo Q4W up to Week 12 followed by 400 mg of peresolimab Q4W, and
- placebo Q4W up to Week 12 followed by 1000 mg of peresolimab Q4W.

Participants randomly assigned to placebo Q4W at Week 0

At Week 12, participants receiving placebo Q4W will begin receiving either 400 mg or 1000 mg peresolimab Q4W based on randomization at Week 0. Treatment assignment will be blinded, and the participants will continue their assigned peresolimab dose and dosing frequency until the end of the study.

Participants randomly assigned to 100 mg peresolimab at Week 0

Participants receiving 100 mg peresolimab will continue their assigned dose and dosing frequency throughout the duration of the treatment period. No changes will occur.

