4.6.1. Extent of Exposure

Duration of exposure to study drug during the double-blind treatment period will be summarized by treatment arm and provided as listing. Duration of exposure on treatment will be calculated as the date of last dose of study drug (or date of discontinuation) minus the date of first dose of study drug plus 1 day. Total patient-years (PYs) of exposure will be reported for each treatment group for overall duration of exposure. Descriptive statistics (n, mean, SD, minimum, maximum, first quartile, median, third quartile, and maximum) will be provided for patient-days of exposure and the frequency of patient falling into different exposure ranges will be summarized. Exposure ranges are as follows:

- $>0, \ge 12$ weeks, ≥ 24 weeks, and ≥ 60 weeks
- >0 to <12 weeks, ≥12 weeks to <24 weeks, ≥24 weeks to <60 weeks, and ≥60 weeks

Overall exposure will be summarized in total PYs, which will be calculated as follows:

Exposure in patient years = $Sum \ of \ duration \ of \ exposure$ (for all patients in treatment arm) / 365.25.

No inferential analysis for comparison between treatment arms will be performed.

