4.6.2.2. Allergic Reactions and Hypersensitivities

The current standard MedDRA Standardized Medical Queries (SMQs) to search for relevant events will be used. TEAEs are characterized as follows:

- Anaphylactic reaction SMQ (20000021)
- Hypersensitivity SMQ (20000214)
- Angioedema SMQ (20000024).

The frequency and percentage of patients experiencing treatment-emergent hypersensitivities will be summarized by treatment arm, SMQ, and PT during the Treatment Period. The frequency and percentage of patients experiencing treatment-emergent hypersensitivities will also be summarized by treatment arm and timing category.

Exposure-adjusted incidence rates (per 100 PYs) of treatment-emergent hypersensitivities will be summarized.

Total number of patients who experienced the TEAE for each PT while they were on Peresolimab will be divided by the sum of all patients' time (in 100 years) of Peresolimab

exposure during the treatment period. The entire time on the study during the Peresolimab treatment period will be used to calculate the patient's time of exposure.

The time to onset of first treatment-emergent hypersensitivity during the Treatment Period and the duration of each treatment-emergent hypersensitivity during the Treatment Period will also be defined and calculated in the same way.

A by-patient listing of all treatment-emergent hypersensitivities will be provided.

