4.6.2.5. Malignancies

Malignancies will be defined using terms from the Malignant tumors SMQ (20000194) or Malignancies SMQ (20000090).

The frequency and percentage of patients with a treatment-emergent malignancy will be summarized by treatment arm, maximum severity, SOC, and PT during the Treatment Period. Exposure-adjusted incidence rates (per 100 PYs) for each type of treatment-emergent malignancy will be presented by treatment arm, and PT during the Treatment Period. AEs will be summarized under a particular time interval if they started or worsened on or after the interval start date and before the interval end date.

Malignancies excluding nonmelanoma skin cancers (NMSC) and NMSC will be also reported separately. NMSC will be defined using the below PTs:

- Squamous cell carcinoma of skin (10041834)
- Bowen's disease (10006059)
- Basal cell carcinoma (10004146)
- Basosquamous carcinoma (10004178)
- Basosquamous carcinoma of skin (10004179)
- Squamous cell carcinoma (10041823)
- Skin squamous cell carcinoma metastatic (10077314)
- Skin cancer (10040808)
- Carcinoma in situ of skin (10007390)
- Keratoacanthoma (10023347)
- Vulvar squamous cell hyperplasia (10079905)
- Skin squamous cell carcinoma recurrent (10081136)
- Lip squamous cell carcinoma (10064055)
- Penile Squamous cell carcinoma (10059631)

The time to onset of first treatment-emergent malignancies during the Treatment Period will be summarized in the same way as time to onset of first treatment-emergent infections.

A by-patient listing of treatment-emergent malignancies will be provided.

Additional information will be provided in the Adjudication Committee Charter.

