4.9. Changes to Protocol-Planned Analyses

There is no change to protocol-planned analyses.

5. Sample Size Determination

Approximately 420 participants CCI

- 100 mg of peresolimab Q4W
- 400 mg of peresolimab Q4W
- 1000 mg of peresolimab Q4W
- Placebo to 400 mg of peresolimab Q4W, or
- Placebo to 1000 mg of peresolimab Q4W.

CCI

- At Week 12, the 100 mg peresolimab treatment group will have a sample size of approximately 60 participants, and the 400 mg and 1000 mg peresolimab treatment groups will each have a sample size of approximately 120 participants.
- At Week 12, the placebo group will have a sample size of approximately 120 participants.

6. Supporting Documentation

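### The exposure-adjusted incidence rate counts patients over all their time on study, including time after the first event and, read literally, after study drug stops; the rate is diluted slightly and SAP 4.6.1 and 4.6.2.2 disagree.

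*SAP*

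**What the plan says.** SAP 4.6.2.2 announces the measure: "Exposure-adjusted incidence rates (per 100 PYs) of treatment-emergent hypersensitivities will be summarized". It then defines it. The numerator is a count of patients and the denominator is peresolimab exposure summed over everyone, in units of 100 years: "Total number of patients who experienced the TEAE for each PT while they were on Peresolimab will be divided by the sum of all". The denominator is spelled out: "The entire time on the study during the Peresolimab treatment period will be used to calculate the" patient's exposure. No rule ends a patient's time at the event. The SAP version history records that Version 3 clarified how these rates are calculated, so the wording is deliberate.

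SAP 4.6.1 defines exposure differently. There, duration is "calculated as the date of last dose of study drug (or date of discontinuation) minus the date of first dose of study drug", plus one day.

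Two other sections plan the same type of rate without a formula of their own. SAP 4.6.2.5 says "Exposure-adjusted incidence rates (per 100 PYs) for each type of treatment-emergent malignancy will be presented by treatment arm, and PT during the Treatment Period". SAP 4.6.2.6 plans such rates for depression and also splits them by time interval.

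Protocol 7.1 lists a systemic hypersensitivity reaction related to administration among the reasons for permanently stopping study intervention, and encourages anyone who stops to remain in the study. The escape criteria in SAP 1.2 likewise let participants stay on after permanent discontinuation.

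**The concern.** An incidence rate normally divides first events by time at risk of a first event. An event rate divides all events by all time. The SAP takes its numerator from the former and its denominator from the latter. Once a patient has had the event, further follow-up enlarges the denominator and cannot enlarge the numerator.

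There is also a mismatch of windows. The numerator is limited to events on peresolimab, but time on study continues for participants who stop the drug and stay. Two programmers, one following 4.6.1 and one following the letter of 4.6.2.2, could report different rates. Hypersensitivity and malignancy are both adverse events of special interest (SAP 4.6.2), so the figure should have one meaning and a label that fits it.

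**Working it through.** The documents give no expected incidence, onset time or rate, so there is no planned figure to reproduce. Incidences and onset times below are assumptions, shown over a range.

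**Inputs.** The Treatment Period is 60 weeks (SAP 1.2). In years of 365.25 days (SAP 4.6.1), T = 420/365.25 = 1.150. Participants who start on placebo have 48 weeks on peresolimab. The 400 mg and 1000 mg groups have about 120 participants each (SAP Section 5).

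**Direction.** The planned rate is n / (sum of all time). The first-event rate is n / (sum of time to first event, or to end of window). The numerator is the same and the first denominator is never the smaller, so the planned rate is never the higher. The two are equal if no patient accrues counted time after the event.

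**Size.** Let p be the proportion with an event by Week 60, with everyone followed to Week 60.

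- Planned rate = 100p/T.
- Under constant hazard, first-event rate = 100 × (−ln(1−p))/T, so planned / first-event = p/(−ln(1−p)).
- With mean onset at Week m, shortfall = p(60−m)/60. For m = 6 this is 0.9p.

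| p | Planned, per 100 PY | First-event, constant hazard | Shortfall, constant hazard | Shortfall, mean onset Week 6 |
|---|---|---|---|---|
| 1% | 0.87 | 0.87 | 0.5% | 0.9% |
| 2% | 1.74 | 1.76 | 1.0% | 1.8% |
| 5% | 4.35 | 4.46 | 2.5% | 4.5% |
| 10% | 8.70 | 9.16 | 5.1% | 9.0% |
| 20% | 17.39 | 19.41 | 10.4% | 18.0% |

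**The two exposure definitions.** Take 120 patients, of whom 12 react at Week 6 (0.115 years), stop the drug and stay in the study to Week 60.

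- Literal 4.6.2.2: 12/(120 × 1.150) = 12/138.0, or 8.70 per 100 PY.
- 4.6.1, with exposure ending when the drug stops at Week 6: 12/(108 × 1.150 + 12 × 0.115) = 12/125.6, or 9.56 per 100 PY.

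The gap is 9.0% and comes entirely from 54 off-drug weeks for each of 12 patients. Off-drug time of event-free patients who stay in the study would dilute the literal version further.

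**Comparison of arms.** With constant hazard in both arms, 10% against 5% gives a ratio of 2.00 planned and 2.05 first-event; 20% against 10% gives 2.00 and 2.12. The narrowing is not guaranteed. Suppose one arm has 5% incidence with onset at Week 4 and another 7% with onset at Week 45. The shortfalls are 0.05 × 56/60 = 4.7% and 0.07 × 15/60 = 1.8%, so the arm with fewer events is diluted more. The planned ratio is 0.07/0.05 = 1.40 and the first-event ratio is 1.40 × (1−0.0467)/(1−0.0175) = 1.36, so here the planned ratio is the wider.

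**The case against.** The strongest reply is that the SAP states openly what it will compute. Patients per unit of total exposure is a usable descriptive measure, and calling it low presupposes a first-event rate that the SAP does not say it is estimating. That stands as far as it goes. What remains is that the result is labelled an incidence rate, and that its denominator disagrees with 4.6.1.

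The reply on size is also sound. The rate is computed per preferred term, and most terms will be uncommon. At 5% of 120 patients (6 patients) the constant-hazard shortfall is 2.5%, while one patient more or fewer moves the rate by 1/6, about 17%. At 12 patients the shortfall is 5.1%, against an exact Poisson 95% interval of roughly −48% to +75%.

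Nor does this figure stand alone. No between-treatment comparison is planned for the Treatment Period (SAP Table KDAF.3.1). For hypersensitivity, 4.6.2.2 also plans counts and percentages, timing categories, time to first onset and a patient listing. Malignancy has time to first onset in the manner of the infection analysis, which uses censoring and Kaplan-Meier estimates.

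A reader might further infer a mismatch because SAP 4.6.2 allows a TEAE to begin up to 50 days after discontinuation while this numerator does not. The documents do not support that as an error: 4.6.2.2 deliberately limits the numerator to events on peresolimab. Adding later events without adding the corresponding time would create a mismatch.

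**Conclusion.** The definition should be corrected, at low severity. Following 4.6.2.2 as written gives a figure that is equal to or below the first-event rate, and its denominator conflicts with 4.6.1 for anyone who stops the drug and stays in the study. The size is about 0.5 to 2% at 1 to 2% incidence, 2.5 to 4.5% at 5%, and 5 to 9% at 10%. The lower ends assume constant hazard, the upper ends mean onset at Week 6, and both assume that everyone is followed and counted to Week 60. Larger shortfalls require incidences of 20% or more, which nothing in the documents suggests for a single preferred term. The point therefore bears mainly on common or pooled terms.

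Two stronger conclusions are tempting. One is that the arms with most events are always diluted most; that needs similar onset timing and post-event retention across arms, which the documents do not establish. The other is that a safety signal would be concealed; the accompanying percentages, onset summaries and listings make that unlikely. It is also an inference, though a natural one, that the malignancy and depression rates use the same formula, since their sections state none.

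**What to change.** - In SAP 4.6.2.2, for the patient-based rate, end each patient's time at the first event of that term, and otherwise at the end of a single on-peresolimab at-risk window. Define that window once, use it for numerator and denominator alike, and reconcile it with the exposure definition in 4.6.1. For participants who start on placebo, the window should begin at their first peresolimab dose.
- If total exposure is kept, label the rate as total-exposure based and add the rate censored at first event for the adverse events of special interest.
- State in 4.6.2.5 and 4.6.2.6 that the same rule applies. For the depression rates by time interval, say whether a patient with an earlier event remains in later denominators.

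The cost is SAP wording and minor reprogramming. First-onset dates are already needed for the hypersensitivity and malignancy summaries; for depression they would be taken from the recorded adverse event dates. Reported rates would be slightly higher than under the present rule.

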4.6.2.3. Injection Site Reactions

Injection site reactions will be defined using terms from the injection site reactions high level term. Injection site reactions will be captured in the eCRF as an AE.

The frequency and percentage of patients with a treatment-emergent injection site reaction will be summarized by treatment arm, maximum severity, SOC, and PT during Treatment Period.

The frequency and percentage of patients with injection site reactions will be summarized by treatment arm and by the following categories:

- Erythema
 - Severity (Noticeable but Very Mild Redness, Clearly Red, Bright Red, Dark with Ulceration or Necrosis at the Injection Site)
 - o Size (Barely Noticeable, Slight, Moderate, Severe)
- Induration
 - o Severity (Barely Noticeable, Slight, Moderate, Severe)
- Pain
 - o Severity (Mild, Moderate, Severe)
- Pruritus
 - o Severity (Mild, Moderate, Severe)
- Edema
 - o Severity (Mild, Moderate, Severe)

A by-patient listing of treatment-emergent injection site reactions will be provided.

4.6.2.4. Infections

Infectious events include infections, serious infections, opportunistic infections, infections that require therapeutic intervention, and any events involving reactivation of tuberculosis or hepatitis. Such events will be selected using the 'Infections and Infestations' SOC.

Summary of Opportunistic Infections based on MedDRA PTs after the potential opportunistic infections are reviewed by medical and confirmed as opportunistic infections. Listing of Opportunistic Infections based on MedDRA PTs during the study.

- b. Localized herpes zoster infections are not considered OI; only multidermatomal and/or disseminated infections are considered OI.
 - a. Localized or nonmultidermatomal are defined as involvement of the primary and/or adjacent dermatomes only. These may be complicated or uncomplicated:
 - Complicated: documented ocular (cornea or deeper structure; for example, iritis, keratitis, retinitis, and so on) or motor nerve involvement (for example, palsy). Postherpetic neuralgia does not meet criteria for motor nerve involvement.
 - ii. Uncomplicated: localized or nonmultidermatomal cases that are not complicated.
 - b. Multidermatomal is defined as involvement beyond primary and adjacent dermatomes (that is, 4 or more contiguous dermatomes) or involvement of 2 or more noncontiguous dermatomes. These may be complicated or uncomplicated.
 - i. Complicated: documented ocular (cornea or deeper structure; for example, iritis, keratitis, retinitis, and so on) or motor nerve development.
 - ii. Uncomplicated: multidermatomal cases.
 - c. Disseminated: systemic infection, visceral, or widespread cutaneous (for example, 5 or more dermatomes or from 3 to 4 dermatomes including at least 1 noncontiguous [nonadjacent]).
 - d. Recurrent: Herpes zoster (HZ) infection is considered an opportunistic infection irrespective of number of dermatomal involvement when it recurs. Recurrent HZ is defined as either a reported HZ infection in the patient's medical history or prior to the study initiation, with at least one additional event occurring during the course of participation in the study. Alternatively, if there is no reported prior history of HZ, recurrent HZ is characterized by more than one HZ infection in an individual patient during the course of participation in the study.

The frequency and percentage of patients experiencing infectious AEs will also be summarized by treatment, maximum severity, SOC, and PT during the Treatment Period.

A listing of patients with detectable hepatitis B virus (HBV) DNA will be provided.

HBV DNA status (not detectable, detectable but not quantifiable [that is, <lower limit of detection (LLOD)], quantifiable [that is, ≥LLOD]) will be summarized, stratified by applicable baseline HBV serology status.

A summary table of herpes zoster will be provided, including event maximum severity, seriousness, whether resulting in temporary study drug interruption, whether resulting in study drug discontinuation, and event outcome. See Appendix 10 (Section 6.10) for PT list for herpes zoster.

A summary table of herpes simplex will be provided, including event maximum severity, seriousness, whether resulting in temporary study drug interruption, whether resulting in study drug discontinuation, and event outcome. See Appendix 10 (Section 6.10) for PT list for herpes simplex.

The time to onset of first treatment-emergent infectious AE during the Treatment Period will be defined as follows:

```
Time to onset of first treatment-emergent infectious AE (in weeks) = (Start\ date\ of\ first\ infectious\ AE - Date\ of\ first\ injection\ +1)/7.
```

Note that if an infectious AE was preexisting prior to the date of first injection and subsequently became treatment-emergent due to worsening post-baseline, the date of worsening will be used in place of the AE start date.

If a patient does not have a treatment-emergent infectious AE during the Treatment Period, they will be censored at the date of completion or ED from the Treatment Period. Kaplan-Meier estimates of the proportion of patients not yet experiencing their first treatment-emergent infectious AE at 12, 24, 36, 48, and 60 weeks will be provided for each treatment arm. A Kaplan-Meier plot of the time to onset will be presented by treatment arm.

The duration of each treatment-emergent infectious AE during the Treatment Period will be defined as follows:

```
Duration of treatment-emergent infectious AE (in weeks) = (End date of AE – Start date of AE + 1) / 7.
```

If an AE has not ended by the date of completion or ED from the study, including the Posttreatment Follow-up Period, it will be censored as of that date. Descriptive statistics for the duration of treatment-emergent infectious AEs will be summarized by treatment arm. If a patient has more than 1 treatment-emergent infectious AE during the Treatment Period, then each AE will contribute to the analysis. If a patient does not have a treatment-emergent infectious AE during the Treatment Period, they will not be included in the analysis.

A by-patient listing of treatment-emergent infections will be provided.

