4.1. General Considerations

Statistical analysis of this study will be the responsibility of sponsor or its designee. A detailed SAP describing the statistical methodologies will be developed by the sponsor or its designee.

Handling of missing, unused, and spurious data are addressed prospectively in the overall statistical methods described in the protocol and in the SAP, where appropriate. Adjustments to the planned analyses are described in the final clinical study report (CSR).

Baseline for the Treatment Period is defined as the last nonmissing assessment on or prior to the date of the first injection of study treatment for efficacy, unless otherwise specified. In most cases, this will be the measure recorded at Week 0 (Visit 2). For safety analyses, baseline will be defined by period as last nonmissing assessment prior to the first dosing of each period. The Treatment Period starts after the first injection and ends on date of Visit 18 (Week 60) or early discontinuation (ED). Any assessment collected after the first injection is defined as postbaseline for the Treatment Period. If ET visit does not occur, last injection date will be considered as the end of the treatment period. Baseline for safety analysis of the Posttreatment Follow-Up period (Period 4) is defined as the last nonmissing assessment prior to entering Period 4, that is date of Visit 18 (Week 60) or ET.

During this study, data issue was identified for the collection date/time of the electronic clinical outcome assessments (eCOA). Same analysis visit was assigned to eCOA assessment with different collection date than the corresponding visit date. Because of this, study team came up with a method to handle this data issue, which is the analysis visit numbers for electronic clinical outcome assessments (eCOA) data will be assigned based on the actual visit date recorded in the electronic case report form (eCRF). If the eCOA assessment date is within +/- 3 days window of the actual visit, then the analysis visit number of the eCOA assessment will be assigned as the actual visit number. If the eCOA assessment date is outside +/- 3 days window of all the actual visits, then the analysis visit of the eCOA assessment will be considered as unscheduled visit. The eCOA data will be used for the analysis only when the analysis visit number of the eCOA assessment is identical to the visit number captured in the eCOA system.

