4.6.2. Adverse Events

AEs are recorded in the eCRF. Each AE will be coded to System Organ Class (SOC) and Preferred Term (PT), using the *Medical Dictionary for Regulatory Activities* (MedDRA) version that is current at the time of database lock. Severity of AEs is recorded as mild, moderate, or severe.

A treatment-emergent adverse event (TEAE) is defined as an event that first occurred or worsened in severity after baseline and on or prior to the earliest of the visit study drug disposition dates or the last visit date during the treatment period, whichever occurred first, and up to 50 days after study treatment discontinuation. Baseline for Period 2 is defined as all preexisting conditions recorded at Visit 1 and any AEs recorded before the first dose of study intervention. Baselines for other periods are defined as unresolved AEs just prior to the first dose of each period. The MedDRA Lowest Level Term (LLT) will be used in defining which events

are treatment-emergent. The maximum severity for each LLT will be used as baseline. If an event is preexisting during the baseline period for Period 2, but it has missing severity, and the event persists during the treatment period or up to 50 days after treatment discontinuation, then the baseline severity will be considered mild for determining any postbaseline treatment-emergence (that is, the event is treatment-emergent unless the severity is coded mild at postbaseline). If an event occurring postbaseline has a missing severity rating, then the event is considered treatment-emergent. Should there be insufficient data for an AE start date to make this comparison (for example, the AE start year is the same as the treatment start year, but the AE start month and day are missing), the AE will be considered treatment-emergent. For events occurring on the day of the first dose of study treatment, Week 0 (V2) in most cases, the events will be assumed to occur posttreatment and considered as TEAE. For events occurring on the day of doses except for the first dose of study treatment, the events will be considered to occur prior to the study drug injection.

In general, summaries will include the number of patients in the safety population (N), frequency of patients experiencing the event (n), and relative frequency (that is, percentage; n/N*100).

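### For participants who leave with no early discontinuation visit, the special-interest safety tables close on the last injection day, short of the SAP's own 50-day treatment-emergent window

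*SAP*

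**What the plan says.** Three parts of the SAP bear on this.

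- **Which events count.** SAP 4.6.2 extends the treatment-emergent definition past the treatment visits: "and up to 50 days after study treatment discontinuation".
- **When the Treatment Period ends.** SAP 4.1 ends it at Visit 18 (Week 60) or at early discontinuation, and adds: "If ET visit does not occur, last injection date will be considered as the end of the treatment period". The ET visit is what the SAP otherwise calls the ED visit.
- **Which window the special-interest outputs use.** Hypersensitivities are to "be summarized by treatment arm, SMQ, and PT during the Treatment Period". For infections, "infectious AEs will also be summarized by treatment, maximum severity, SOC, and PT during the Treatment Period". For malignancies, "patients with a treatment-emergent malignancy will be summarized by treatment arm, maximum severity, SOC, and PT during the Treatment Period", and the exposure-adjusted malignancy rates use the same period. For time to first infection, participants with no event are handled thus: "they will be censored at the date of completion or ED from the Treatment Period". Malignancy onset follows the infection method.

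None of SAP 4.6.2.2, 4.6.2.4 or 4.6.2.5 adds the 50 days back. The 50-day extension of the TEAE definition is the SAP's own; Protocol 9.3.5 simply takes the treatment period as post-baseline.

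**The concern.** An event that ends dosing will usually start after the last injection, and the last-injection rule closes the window just before it. Protocol 7.1.3 lets a dose be withheld for any acute infection, and Protocol 7.1 stops drug for a related systemic hypersensitivity reaction. Protocol 7.2 asks for ED procedures only where possible, so some participants can be expected to leave without that visit. Protocol 8.3.1 collects AEs until participation ends, so AE data can exist after the last injection.

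SAP 4.6 makes the safety summaries descriptive, so the counts are themselves the result. Hypersensitivity, infections and malignancy are all named in SAP 4.6.2 as adverse events of special interest. Two programmers working from this text could count different events for the same table, and for an early leaver the event in dispute could be the one that stopped treatment.

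**Working it through.** The plan gives no figure on this point, so there is none to reproduce. The check is a comparison of two windows, with date arithmetic.

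**Inputs.** 50 days (SAP 4.6.2); Treatment Period closed on the last injection date if there is no ED visit (SAP 4.1); dosing intervals of 28 days (Q4W) and 84 days (Q12W, possible only from Week 24, SAP 1.2); 420 participants (SAP 5). Assumption: discontinuation is dated at the last injection. A later date would lengthen the omitted stretch by the gap.

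**Days omitted for one participant with no ED visit.** Count the first injection as Day 1. With the last injection at Week w, the Treatment Period closes on Day 7w + 1 and the TEAE window runs to Day 7w + 51.

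| Last injection | Treatment Period closes | TEAE window ends | Share of TEAE window omitted |
|---|---|---|---|
| Week 0 | Day 1 | Day 51 | 50/51 = 98% |
| Week 4 | Day 29 | Day 79 | 50/79 = 63% |
| Week 8 | Day 57 | Day 107 | 50/107 = 47% |
| Week 52 | Day 365 | Day 415 | 50/415 = 12% |

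These are shares of calendar days for a hypothetical participant, not shares of events.

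**Is this off-drug time?** Mostly not. On Q4W, 28 of the 50 days lie inside the dosing interval: 28/50 = 56%. On Q12W all 50 do, since 50 < 84.

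**Worked case.** Doses at Weeks 0, 4 and 8; a non-serious infection starting on Day 71; the Week 12 dose withheld; then withdrawal with no ED visit.

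- Under SAP 4.6.2 the infection is treatment-emergent, because 71 is below 107.
- Under SAP 4.1 the Treatment Period closed on Day 57, so the infection falls outside the SAP 4.6.2.4 table.
- On the time-to-onset curve the participant is censored at 57/7 = Week 8.1. The onset would be at 71/7 = Week 10.1, and the TEAE window runs to 107/7 = Week 15.3, past the Week 12 landmark.

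An event on the day of the last injection itself is kept, so an immediate same-day reaction is not lost.

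**Size across the trial.** The documents do not give the number leaving with no ED visit. Assumed range:

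- 1% of 420, about 4 participants: 4 × 50/365.25 = 0.5 patient-years
- 5%, 21 participants: 21 × 50/365.25 = 2.9 patient-years
- 10%, 42 participants: 42 × 50/365.25 = 5.7 patient-years

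For scale, 420 participants followed for 60 weeks (420 days) give 420 × 420/365.25 = 483 patient-years, and 5.7/483 is about 1.2%. On this dating of discontinuation the figures are upper limits, because AE data may stop before the 50 days are up. No event count is derived, because the documents give no event rates.

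**The case against.** The strongest reply is that these events are reported elsewhere. The overall TEAE tables in SAP 4.6.2, by SOC and preferred term and by maximum severity, rest on the 50-day definition and are not worded with the Treatment Period limit. Infections are selected by a single SOC, so the infection in the worked case should appear in those tables. The following are not worded with the limit either: AEs leading to discontinuation or interruption, SAEs (covered through follow-up), the hypersensitivity table by timing category, the by-patient listings, and the opportunistic infection and herpes outputs. Most malignancies will be SAEs under Protocol 10.3.2. All of this stands. A reader might infer that events vanish from the study report; the documents do not support that.

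Next, Protocol 7.1 encourages participants who stop drug to stay for the remaining visits. Those who do so do not trigger the last-injection rule. It would therefore be wrong to infer that everyone who stops treatment is affected.

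Third, the Treatment Period may be only a display label for Weeks 0 to 60, as in SAP 1.2 and Table KDAF.3.1, with the word treatment-emergent importing the 50 days. That reading is possible, but the SAP does not state it, and the infection sentence does not use the word. The SAP does name follow-up in places, for example in censoring AE duration "by the date of completion or ED from the study, including the Posttreatment Follow-up Period". That is weak evidence for the literal reading, since it concerns how long an event lasts, not which events count.

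Finally, limiting both events and person-time to the Treatment Period keeps rates internally matched and is close to Protocol 9.3.5. That is true, but with the last-injection rule a participant dosed once contributes a single day.

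**Conclusion.** The point holds for one group: participants who stop early with no ED visit. For them the literal text closes the special-interest tables and the onset censoring on the last injection day, while the SAP's own definition runs 50 days further, and at least 28 of those days are still within a dosing interval. It is an inconsistency within the SAP, not a departure from the protocol.

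The omitted share is large for an affected participant but small for the trial: about 0.5 to 5.7 patient-years at most if 1% to 10% leave this way, with discontinuation dated at the last injection. In practice it concerns non-serious events, mainly infections. No primary or inferential result changes.

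A reader might extend the point to the off-drug time of participants who complete Week 60. The documents do not support that: it is Period 4 time, Protocol 9.3.5 says that follow-up emergent AEs will be summarized, and Table KDAF.3.1 has a Follow-up Population row. This merits a clarification, not a redesign.

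**What to change.** In SAP 4.1, 4.6.2.2, 4.6.2.4 and 4.6.2.5, state that when there is no ED visit the AE window does not end on the last injection date. Run event counting, person-time and censoring to the earlier of (a) 50 days past discontinuation of study treatment and (b) the last date with AE data. Define which date counts as discontinuation. The special-interest outputs would then agree with the TEAE definition in SAP 4.6.2.

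The cost is a few sentences and rerun tables on data already collected. The one drawback is that a little off-drug time enters the rates; showing the Treatment Period figures alongside deals with that.
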